# Eligibility Survey, Consenting and Enrollment Procedures

Interested persons will complete eligibility questions on a HIPAA-protected secure web platform. Those not eligible will be directed to medically-vetted website that includes information about anal cancer (e.g., http://www.thebottomline.org.au/). Those eligible will be contacted by staff to arrange a remote consenting session.

The consent form will include detailed information on study activities, including anal canal swabbing and HRA-directed biopsies, and the rationale behind the study. For example, participants will be told that an anal canal screening program of this type would only be useful if persons provided swabs over a period of one year; thus, we are asking them to provide a swab at the beginning of the study and 12 months later.

After consenting, participants will provide contact data including name, phone number, alternate phone number, street address, email address, preferred method of contact and alternate contact information in case primary phone, email, or street address changes. Then, persons will complete the baseline survey.

Those persons with no web access will be encouraged to call study offices for study and eligibility information after which they will be invited for consenting at study offices in which social distancing will be observed and personal protective equipment will be employed. Persons who decide not to consent will be thanked for their time and will be asked if they would like to be directed to a website with information about anal cancer, e.g., http://www.thebottomline.org.au/. After collection of contact information, all participants will be asked to complete a baseline CASI remotely. Persons who successfully complete select CASI questions, i.e., those deemed crucial to study validity, will be considered officially enrolled.

#### PARTICIPANT RANDOMIZATION

Persons officially enrolled will be randomized in a 1:1 allocation to either the home- or clinic-based swabbing. Blocked randomization is not necessary due to sample size. The Houston Data Coordinating Center will prepare randomization lists using Stata Version 13 (College Station, TX). The randomization process will occur for a consented participant who has satisfactorily completed the baseline CASI. Given obvious differences of each arm, randomization cannot be blinded to study staff or participants although participant data including study arm will be blinded to lab staff.

#### PARTICIPANT ACTIVITIES

## **Self-Swabbing Kits**

After completing the CASI baseline survey, participants will get information about receiving a swabbing kit in the mail or making a clinic appointment. Participants in arm 1 will be sent a kit within 2 weeks while those in arm 2 will be asked to attend a clinic appointment in the next 2 weeks. Persons in arm 2 will be provided with names and contact information for a participating clinic and asked to call that clinic to set up an appointment. If they have not made an appointment within 48 business hours, they will be contacted up to three times and asked to make the appointment. Clinic or study staff (depending on clinic) will then contact participants within 24 business hours if the participant does not show for an appointment. Clinic staff will attempt to contact participants 3 times over one month before being classified as non-compliant for Visit 1.

A mock-up of the arm 1 self-swabbing kit will be pre-tested with the CAB. The kit box will not be identifiable as having health-related contents. Shipments will be logged, and the arm 1 participant will be notified upon shipment. Participants not confirming kit receipt within 7 days will be prompted about the kit receipt. The kit will include return packaging, instructions for returning the sample, self-sampling instructions, a biohazard bag, a swab, and a vial of 2 mL of standard transport media (STM) pre-labeled with a participant unique ID, and kit # (i.e., kit 1 or 2). STM is classified as a non-hazardous substance. To assess specimen exposure to extreme temperatures during mail transit, the kit will be packaged within insulation (e.g., Styrofoam) and include a temperature-monitoring device (LogTag Recorders, Auckland, New Zealand).

Home-based participants' kits will include instructions for self-swabbing written at a 6th-grade reading level in either English or Spanish. The instructions will be modeled after already-tested self-sampling instructions and presented to the CAB.

After receipt of the kit, participants will be instructed to wash hands with soap and water. The instructions will ask the participant to get into a comfortable position (e.g., one foot on a toilet), hold the swab in their dominant hand, pull back a buttock with the other hand and then insert the swab gently into the anal canal about 2-3 inches. The participant will then twirl the swab, count slowly to 10, and remove the swab, all the while applying swab pressure to the anal canal walls. After collecting the specimen, persons will place the swab into the tube, and then place the tube into the biohazard bag.  Kit instructions will ask participants to record the date of the swabbing. Participants will be asked to wait until 24 hours after last receptive anal sex before self-swabbing.

Participants will be asked to return the kit within 3 days by overnight mail to the MCW Tissue Bank. The receipt date will be logged at the MCW Tissue Bank. When MCW receives the kit, the participant will be sent a link to complete the post swab 1 CASI online. Study staff will contact participants who have not returned kits within 2 weeks of kit delivery. Study staff will attempt to contact participants 3 times over one month after kit delivery before recording them as non-compliant.

All persons in the home-based arm 1 will be asked to attend a study clinic of their choice to receive height, weight, and waist circumference measurements, a clinician swab and a DARE to rule out prevalent anal cancer. If there is a finding on DARE, then standard clinical practices will be followed.

## Clinic-Based Swabbing

Participants in Arm 2 will attend an appointment at a participating clinic for biometric measurements (height, weight, and waist circumference) anal canal swabbing, DARE, and computer-assisted self-interviews. Persons will be asked to attend appointments within two weeks after randomization. Appointments will be made that are convenient for the participant and attended by a highly-experienced clinician who will collect exfoliated cells with a swab from the participant using the Darragh swabbing protocol (e.g., twirling the swab, counting slowly to 10, slowly removing the swab, and applying pressure to the anal canal walls) and the same brand of swab as home-based kits. The study staff will put the swabs in an insulated cooler and return them to MCW for immediate processing.

The PI or study coordinator will observe the sampling protocol of the first 3 participants at each clinical site and re-observe on an annual basis.

All persons in the clinic-based arm will receive a DARE after the clinician swabbing to rule out prevalent anal cancer. If there is a finding on DARE, then standard clinical practices will be followed.

## Specimen Storage

All swabs will be stored at the MCW Tissue Bank in O-ringed cryovials after processing by Tissue Bank staff.

#### Swabbing 2 at 12 months and HRA Scheduling

Procedures for kits and clinic appointments at 12 months will mirror baseline procedures. All persons in arm 1 will be reminded 11.5 months after baseline of the shipment of kit #2 or if in arm 2, the need to schedule clinic appointment #2 for clinician-based swabbing. Reminders and communication to all participants will mirror procedures typically used by medical clinics, e.g., birthday greetings and up to four reminders. At the same time, all persons will be scheduled for HRA at the Froedtert/MCW Anal Dysplasia Program. We will make up to four attempts to schedule a person for HRA. For a person who declines the HRA, we will request the reason(s) why. Persons in both arms who are lost to follow up after consenting will still be solicited for a 12-month swabbing and HRA.

# Computer-Assisted Self-Interviews

To accomplish the Aim 2 objective, to assess factors independently associated with MSM and transpersons who return a swab at baseline and 12 months, we will design CASI questionnaires capturing demographics, attitudes, and behavioral data in the baseline survey, after the 0- and 12-month swabbing time points, and after HRA. All participants will complete CASIs in English or Spanish (after translation and back translation) on the HIPAA-compliant secure web platform REDCap (Vanderbilt University). Each CASI will include questions adapted from validated cervical cancer screening survey. For adaptation, the items were modified with the input of co-Investigators, study staff and cognitive interviews with the target community. The surveys have subscales that can be used independently if any of the psychometric properties of the subscale indicate that it is not a reliable or valid measure of the construct. Since participants will complete CASIs in the study spanning the time from baseline CASI to post-HRA CASI, changes in participants' attitudes to swabbing or HRA will be captured.

The baseline survey conducted remotely after consenting will record demographics of the study entry population including anal cancer anxiety, prior experience with anal cancer, prior experience with other anal diseases, self-sampling acceptability, prior anal cancer screening (including HRA), benefits/barriers of anal cancer screening, and sexual behavior.

Participants will complete another CASI after each swabbing. Participants will be asked about the experience of self-sampling/clinician sampling and DARE within the framework of HBM constructs. 44,71 Experience with DARE will be asked of Arm 1 participants at the end of their clinic DARE visit. Other CASI items will cover kit mailing, kit return, kit appearance, kit materials, and trust in the clinician (depending on study arm). The CASIs will include anxiety-related questions about anal cancer screening and the annual screening interval.

Participants will complete a final short CASI to assess the acceptability of HRA like perceived barriers (embarrassment) in addition to prior anoscopy experiences, the perception of pain, and knowledge of HRA availability.

Persons in either arm who are uncomfortable using computers or do not have access to technology will be assisted by staff in study offices to complete the CASI (or provided a mailed paper copy if a participant in the home-based arm prefers). In our prior R21, ~2% of participants required such assistance.

To determine the proportion of consented persons who would be interested in a follow-up or renewal anal cancer study, all persons who consented to the parent study will be contacted near study end. Persons will be contacted by the email or phone number provided by them in the parent study. If necessary, non-respondents will be contacted up to 3 times starting with their preferred method of contact for the first two contacts and switching to another method for the third contact. After asking the one question in this effort (see Renewal Survey file), we will record a Yes or No in the appropriate REDCap field to record their interest in a future study.

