# Medical Records

All participants will have their medical record reviewed for HPV-associated procedures or conditions. From the medical records of persons with HIV, we will abstract viral load and CD4 count information. Findings will be systematically recorded using a standardized data extraction form. All persons who are not verified as HIV-positive through medical records will receive an HIV test at the baseline clinic visit and one year later at HRA. Standard clinical practices will be followed for providing HIV test results and any needed subsequent care.

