#### EPIDEMIOLOGICAL AND STATISTICAL CONSIDERATIONS

#### Analysis

Participants will be randomized to either Arm 1 or Arm 2. For Aim 1 our primary analysis is to compare the proportion of those who comply with 0 and 12-month swabbing in the home- and clinic-based arms. Our primary endpoint, compliance, is categorized as "Yes" if a swab is returned at 0 and 12 months and "No" otherwise. The null hypothesis is that the proportion of those complying in each arm is the same. Under the intention-to-treat principle, all participants who are randomized are included in the analyses (primary and exploratory). We will compare the proportion of persons who are compliant in the two arms using a Mantel-Haenszel test for difference in proportions in a stratified design ( $\alpha$ =0.05). For sensitivity analysis we will also do a per protocol analysis comprised of compliant participants.

Participants will be considered non-compliant for either baseline or 12-month swab if they do not provide a swab within 30 days after kit mailing or clinic appointment. Persons randomized to arm 1 who "crossover" and attend a doctor's visit for anal cancer screening, including DNA collection, without returning a home-base kit, will be counted as non-compliant.

For Aim 2, to determine factors associated with compliance, we will use purposeful modeling strategies. We will perform a bivariate logistic regression for each factor, and those factors with a p-value less than 0.25 in the bivariate analysis will be included in a multivariable logistic regression model. Given that we expect 144 and 108 12-month swabs returned from arm 1 and arm 2, respectively, we can safely examine up to 10 factors simultaneously in the model and maintain the recommended minimum of 10 events per variable in the multivariable model. We will pay particular attention to the aforementioned HBM constructs, e.g., self-efficacy, to ascertain their ability to explain variance in compliance. Associations in the multivariable model will be considered significant with a p-value of <0.05. Adjusted and unadjusted odds ratios will be

reported with 95% CIs. We will regress compliance on covariates after adjusting for study arm, HIV status, race, and age (i.e., the randomization strata) and potential confounders identified with Directed Acyclic Graphs including insurance status, socioeconomic status and ethnicity.

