# Threats to Validity

For Aim 1 selection bias and loss-to-follow-up are threats to validity; thus, we will recruit without

Table 2. Power to detect odds ratio for varying												
proportion exposed in clinic arm												
Proportion exposed in clinic												
	arm (e.g., HIV+)											
Odds Ratio	0.4	0.5	0.6									
1.50	0.52	0.52	0.49									
1.75	0.79	0.79	0.75									
2.00	0.93	0.92	0.89									
2.25	0.98	0.98	0.96									

reference to home-based screening or HRA to lessen the population of persons with heightened concern and reservations about self-swabbing or HRA. Recruitment will use diverse strategies to select a broad spectrum of MSM and transpersons. Those strategies will be modified if enrolled persons are not racially and ethnically diverse; however, since study participants may still be different than non-participants we will ask participants about enrollment motivation including potential concern about study procedures like HRA.

For Aim 2 our primary CASI instruments will be adapted from validated cervical cancer screening instruments given the absence of validated anal cancer screening instruments. The CASI format will keep information bias and missing data to a minimum. If there are excessive missing data for a covariate, we will use the SAS procedure MI to impute missing values.

For Aim 3, we are keenly aware that selection bias and loss-to-follow-up are threats to validity; thus, questions during eligibility screening and consenting will capture data on reasons for declining study participation and the baseline CASI will provide rich data on those who do not return at 12 months. Specimen validity may suffer if poorly collected or exposed to extreme temperature, but studies find self-swabs generally have high adequacy.

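### The plan assigns post-swab and post-HRA surveys to Aim 2 and does not limit the compliance model to factors measured before randomisation

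*Combined protocol and SAP*

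**What the plan says.** The Computer-Assisted Self-Interviews section presents the questionnaires as the means of meeting the Aim 2 objective, "capturing demographics, attitudes, and behavioral data in the baseline survey, after the 0- and 12-month swabbing time points, and after HRA". The Analysis section counts a participant as compliant "if a swab is returned at 0 and 12 months" and as non-compliant otherwise. It screens factors one at a time at p < 0.25 and carries those that pass into a multivariable logistic model. It singles out Health Belief Model constructs such as self-efficacy and adds: "We will regress compliance on covariates after adjusting for study arm, HIV status, race, and age". It names no survey wave as the source of the factors.

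Delivery of the post-swab surveys is described in three places:

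- Self-Swabbing Kits, for the home arm: "When MCW receives the kit, the participant will be sent a link to complete the post swab 1 CASI online".
- Clinic-Based Swabbing puts the clinic arm's computer interviews in the swab appointment.
- Swabbing 2 at 12 months and HRA Scheduling says the 12-month procedures repeat those at baseline.

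The Incentives section, however, pays all participants for the two post-swab surveys whether or not a swab is returned.

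The baseline survey comes first: "The randomization process will occur for a consented participant who has satisfactorily completed the baseline CASI". The enrolment section adds: "Persons who successfully complete select CASI questions, i.e., those deemed crucial to study validity, will be considered officially enrolled". For gaps, Threats to Validity says: "If there are excessive missing data for a covariate, we will use the SAS procedure MI to impute missing values".

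**The concern.** Read as written, the plan lets post-swab and post-HRA answers into the model for both-swab compliance. Three problems follow.

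- If the survey reaches people because they swabbed, having a value depends on a component of the outcome.
- Answers given at or after the 12-month swab cannot be read as predictors of it, because the experience of complying may have shaped the attitude.
- Questions about the experience of swabbing have no answer for someone who did not swab. Imputing them fills those records from people who did.

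Aim 2 is one of three specific aims and is meant to guide future interventions. An odds ratio for self-efficacy or perceived barriers that partly reflects who received the survey, or reverse causation, would misdirect them.

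**Working it through.** **Inputs** (Sample Size Estimation and Analysis): 200 per arm; swab 1 return 80% home and 70% clinic; 12-month swabs 144 home (72%) and 108 clinic (54%); 10 events per variable; up to 10 factors.

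**Assumptions.** The post-swab survey exists only if that swab was returned, and everyone who receives it completes it. Swabs returned after the 30-day window are ignored; they would give some non-compliers with data, but the plan has no figure for them. The overlap between the two swabs is not given, so it is bracketed: nested (every 12-month returner also returned swab 1) to independent within arm.

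**The plan's own figure.** It counts 144 + 108 = 252 compliers, so 400 − 252 = 148 non-compliers. The smaller class allows 148/10 = 14.8 factors. The stated limit of 10 holds if every participant has the factor.

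**Missing surveys.**

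- Post-swab 1: 200 × 0.20 + 200 × 0.30 = 100 without data, 300 with (160 + 140).
- Post-swab 2: 400 − 252 = 148 without data, 252 with.

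**Non-compliers with data.**

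- Post-swab 1, nested: (160 − 144) + (140 − 108) = 16 + 32 = 48.
- Post-swab 1, independent: compliers are 160 × 0.72 + 140 × 0.54 = 115.2 + 75.6 = 190.8, leaving 300 − 190.8 ≈ 109.
- Post-swab 2, nested: 252 − 252 = 0.
- Post-swab 2, independent: 252 − 190.8 ≈ 61.
- Both surveys in one model: 0 in either case, since having both means having returned both swabs.

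| Source of factors | Persons with data | Non-compliers with data | Factors at 10 per variable |
|---|---|---|---|
| Baseline CASI | 400 | 148 to 209 | 14 to 19 |
| Post-swab 1 CASI | 300 | 48 to 109 | 4 to 10 |
| Post-swab 2 CASI | 252 | 0 to 61 | 0 to 6 |

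For baseline items under independence, non-compliers number 400 − 190.8 ≈ 209, so the smaller class is the 191 compliers.

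**Why a fitted post-swab 1 model can still mislead** (assumed rates, for illustration). Let swab 1 return be 90% with a factor and 70% without, and let 80% of swab 1 returners in both groups return swab 2.

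- Everyone: compliance is 0.90 × 0.80 = 72% and 0.70 × 0.80 = 56%. OR = (0.72/0.28)/(0.56/0.44) = 2.02.
- Post-swab 1 completers only: 80% in both groups. OR = 1.00.

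The share of non-compliers kept is 0.18/0.28 = 64% with the factor and 0.14/0.44 = 32% without. The selection depends on the factor as well as the outcome, and a real predictor disappears.

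**The case against.** The other side has four good arguments.

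**Access.** A reader might infer that only people who returned a swab can complete a post-swab survey. The documents do not support that. Payment is promised regardless of swab return, and staff help or paper copies are offered. This stands: the sections conflict, and the counts above apply only if delivery follows the swab. But no section says how a non-returner would get the survey. Full delivery would also leave the timing problem and the unanswerable experience items.

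**Estimability.** A reader might infer that the Aim 2 model cannot be estimated. As a general statement that is wrong. With baseline factors the model is well supported, and with post-swab 1 items it can be fitted. It fails only for post-swab 2 items under fully nested returns, or if both post-swab surveys enter one model, which no section proposes. It is also true that missingness depending on the outcome alone does not by itself bias logistic odds ratios. Here, though, it depends on one component of the outcome, and the example shows the consequence.

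**Intent.** The survey section's opening may be only an overview. Post-HRA data are assigned to HRA acceptability under Aim 3, and the baseline survey already covers anxiety, acceptability, benefits and barriers, and sexual behaviour. That is a fair reading, but the text does not say so. Self-efficacy, which the Analysis section stresses, is not in the list of baseline content, and the Health Belief Model framework is mentioned with the post-swab surveys.

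**HIV status.** The Medical Records section says: "All persons who are not verified as HIV-positive through medical records will receive an HIV test at the baseline clinic visit". A reader might infer that HIV status, an adjuster, is missing for clinic-arm non-attenders and that its odds ratio is badly distorted. In the clinic arm with 50% HIV-positive, a true OR of 1 and all 30 HIV-negative non-attenders dropped, it would be (54/46)/(54/16) = 0.35. That is a worst case. The same sentence provides a second test a year later at HRA, people lost to follow-up are still invited to HRA, and nothing says the untested would be dropped.

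**Conclusion.** The concern holds in a limited form. The plan names post-swab and post-HRA surveys as a data source for Aim 2 and does not exclude them from the compliance model. If delivery follows the swab, 100 of 400 would lack post-swab 1 data and 148 would lack post-swab 2 data. The non-compliers available would fall from at least 148 to 48–109 and 0–61 respectively. These counts rest on the plan's return rates, full survey completion after a swab, and the nested-to-independent bracket.

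The size of any bias is not known; the change from 2.02 to 1.00 shows only what selection on swab 1 can do. The timing objection to post-swab 2 and post-HRA items does not depend on how the survey is delivered. The documents support neither the conclusion that Aim 2 as a whole is inestimable nor a definite distortion of the HIV odds ratio.

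**What to change.** In the Computer-Assisted Self-Interviews and Analysis sections:

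1. State that candidate factors and adjusters for both-swab compliance, apart from study arm, come only from data collected before randomisation: the eligibility and baseline CASIs, the medical record up to that date, and HIV status as known at enrolment.
2. Use post-swab and post-HRA items descriptively, or for outcomes that come after the survey among those who reached it, such as swab 2 return among swab 1 returners.
3. In Threats to Validity, limit multiple imputation so that swabbing-experience items are not imputed for people who did not swab.
4. Reconcile the delivery text (Self-Swabbing Kits, Clinic-Based Swabbing, Computer-Assisted Self-Interviews) with the Incentives section, and say how, if at all, a non-returner receives a post-swab survey.

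The cost is wording. The scientific price is that post-swab attitudes can no longer be offered as predictors of both-swab compliance. The sponsor should confirm that self-efficacy and HIV status were captured before randomisation. A construct first measured after a swab would drop out of this model.
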